5.3 METHODS AND TIMING FOR CAPTURING AND ASSESSING SAFETY PARAMETERS

The investigator is responsible for ensuring that all adverse events (see Section 5.2.1 for definition) are recorded on the Adverse Event eCRF and reported to the Sponsor in accordance with instructions provided in this section and in Sections 5.4, 5.5, and 5.6. The investigator is also responsible for reporting medical device complaints (see Section 5.4.4).

For each adverse event recorded on the Adverse Event eCRF, the investigator will make an assessment of seriousness (see Section 5.2.2 for seriousness criteria), severity (see Section 5.3.3), and causality (see Section 5.3.4).

5.3.1 Adverse Event Reporting Period

Investigators will seek information on adverse events at each patient contact. All adverse events, whether reported by the patient or noted by study personnel, will be recorded in the patient's medical record and on the Adverse Event eCRF.

After informed consent has been obtained but prior to initiation of study drug, only serious adverse events caused by a protocol-mandated intervention (e.g., serious adverse events related to invasive procedures such as biopsies, *discontinuation of medications*) should be reported (see Section 5.4.2 for instructions for reporting serious adverse events).

After initiation of study drug, all adverse events, regardless of relationship to study drug, will be reported until the patient completes his or her last study visit. After this period, patients who enter the GA28951 study should follow the adverse event reporting requirements of that study.

If the patient does not enter the GA28951 study, the Sponsor should be notified if the investigator becomes aware of any post-study serious adverse events that are believed to be related to prior study drug treatment. In addition, the Sponsor should be notified if the investigator becomes aware of any post-study events of confirmed or suspected PML, regardless of relationship to study drug, for up to 2 years after the patient's last dose of study drug (see Section 5.6).

5.3.2 Eliciting Adverse Event Information

A consistent methodology of non-directive questioning should be adopted for eliciting adverse event information at all patient evaluation timepoints. Examples of non-directive questions include the following:

“How have you felt since your last clinic visit?”

“Have you had any new or changed health problems since you were last here?”

5.3.3 Assessment of Severity of Adverse Events

The adverse event severity grading scale for the NCI CTCAE (v4.0) will be used for assessing adverse event severity. [Table 6](#) will be used for assessing severity for adverse events that are not specifically listed in the NCI CTCAE.

Table 6 Adverse Event Severity Grading Scale for Events Not Specifically Listed in NCI CTCAE

Grade	Severity
1	Mild; asymptomatic or mild symptoms; clinical or diagnostic observations only; or intervention not indicated
2	Moderate; minimal, local, or non-invasive intervention indicated; or limiting age-appropriate instrumental activities of daily living ^a
3	Severe or medically significant, but not immediately life-threatening; hospitalization or prolongation of hospitalization indicated; disabling; or limiting self-care activities of daily living ^{b, c}
4	Life-threatening consequences or urgent intervention indicated ^d
5	Death related to adverse event ^d

NCI CTCAE = National Cancer Institute Common Terminology Criteria for Adverse Events.

Note: Based on the most recent version of NCI CTCAE (v4.0), which can be found at: http://ctep.cancer.gov/protocolDevelopment/electronic_applications/ctc.htm

- ^a Instrumental activities of daily living refer to preparing meals, shopping for groceries or clothes, using the telephone, managing money, etc.
- ^b Examples of self-care activities of daily living include bathing, dressing and undressing, feeding one's self, using the toilet, and taking medications, as performed by patients who are not bedridden.
- ^c If an event is assessed as a "significant medical event," it must be reported as a serious adverse event (see Section 5.4.2 for reporting instructions), per the definition of serious adverse event in Section 5.2.2.
- ^d Grade 4 and 5 events must be reported as serious adverse events (see Section 5.4.2 for reporting instructions), per the definition of serious adverse event in Section 5.2.2.

5.3.4 Assessment of Causality of Adverse Events

Investigators should use their knowledge of the patient, the circumstances surrounding the event, and an evaluation of any potential alternative causes to determine whether an adverse event is considered to be related to the study drug, indicating "yes" or "no" accordingly. The following guidance should be taken into consideration:

- Temporal relationship of event onset to the initiation of study drug
- Course of the event, considering especially the effects of dose reduction, discontinuation of study drug, or reintroduction of study drug (where applicable)
- Known association of the event with the study drug or with similar treatments
- Known association of the event with the disease under study

- Presence of risk factors in the patient or use of concomitant medications known to increase the occurrence of the event
- Presence of non-treatment-related factors that are known to be associated with the occurrence of the event

Table 7 Causal Attribution Guidance

Is the adverse event suspected to be caused by the study drug on the basis of facts, evidence, science-based rationales, and clinical judgment?	
YES	There is a plausible temporal relationship between the onset of the adverse event and administration of the study drug, and the adverse event cannot be readily explained by the patient's clinical state, intercurrent illness, or concomitant therapies; and/or the adverse event follows a known pattern of response to the study drug; and/or the adverse event abates or resolves upon discontinuation of the study drug or dose reduction and, if applicable, reappears upon re-challenge.
NO	An adverse event will be considered related, unless it fulfills the criteria as specified below. Evidence exists that the adverse event has an etiology other than the study drug (e.g., preexisting medical condition, underlying disease, intercurrent illness, or concomitant medication); and/or the adverse event has no plausible temporal relationship to administration of the study drug (e.g., cancer diagnosed 2 days after first dose of study drug).

5.3.5 Procedures for Recording Adverse Events

Investigators should use correct medical terminology/concepts when recording adverse events on the Adverse Event eCRF; the use of colloquialisms and abbreviations should be avoided.

Only one adverse event term should be recorded in the event field on the Adverse Event eCRF.

5.3.5.1 **Diagnosis versus Signs and Symptoms** **Injection-Site Reactions**

Local cutaneous adverse events that occur at or around the injection site during or within 24 hours following study drug injection should be separately captured as individual signs (e.g., erythema, induration/swelling at injection site) or symptoms (e.g., pain, pruritus at injection site) rather than a diagnosis of allergic reaction or injection-site reaction.

Other Adverse Events

For adverse events other than injection-site reactions, a diagnosis (if known) should be recorded on the Adverse Event eCRF rather than individual signs and symptoms (e.g., record only liver failure or hepatitis rather than jaundice, asterixis, and elevated transaminases). However, if a constellation of signs and/or symptoms cannot be medically characterized as a single diagnosis or syndrome at the time of reporting, each individual event should be recorded on the Adverse Event eCRF. If a diagnosis is

subsequently established, all previously reported adverse events based on signs and symptoms should be nullified and replaced by one adverse event report based on the single diagnosis, with a starting date that corresponds to the starting date of the first symptom of the eventual diagnosis.

5.3.5.2 Adverse Events Occurring Secondary to Other Events

In general, adverse events occurring secondary to other events (e.g., cascade events or clinical sequelae) should be identified by their primary cause, with the exception of severe or serious secondary events. Medically significant adverse events occurring secondary to an initiating event that are separated in time should be recorded as independent events on the Adverse Event eCRF. For example:

- If vomiting results in mild dehydration with no additional treatment in a healthy adult, only vomiting should be reported on the eCRF.
- If vomiting results in severe dehydration, both events should be reported separately on the eCRF.
- If a severe gastrointestinal hemorrhage leads to renal failure, both events should be reported separately on the eCRF.
- If dizziness leads to a fall and subsequent fracture, all three events should be reported separately on the eCRF.
- If neutropenia is accompanied by an infection, both events should be reported separately on the eCRF.

All adverse events should be recorded separately on the Adverse Event eCRF if it is unclear as to whether the events are associated.

5.3.5.3 Persistent or Recurrent Adverse Events

A persistent adverse event is one that extends continuously, without resolution, between patient evaluation timepoints. Such events should be recorded only once on the Adverse Event eCRF. The initial severity (intensity or grade) of the event will be recorded at the time the event is first reported. If a persistent adverse event becomes more severe, the most extreme severity should be recorded on the Adverse Event eCRF. If the event becomes serious, it should be reported to the Sponsor immediately (i.e., no more than 24 hours after learning that the event became serious; see Section 5.4.2 for reporting instructions). The Adverse Event eCRF should be updated by changing the event from “non-serious” to “serious,” providing the date that the event became serious and completing all data fields related to serious adverse events.

A recurrent adverse event is one that resolves between patient evaluation timepoints and subsequently recurs. Each recurrence of an adverse event should be recorded separately on the Adverse Event eCRF.

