6.5 SAFETY ANALYSES

The safety analyses will include all patients who received at least one dose of study drug in the Induction Phase. Separate summaries of adverse events will be provided for the open-label Induction Phase and the Maintenance Phase.

Safety will be assessed through descriptive summaries of adverse events, laboratory test results (serum chemistry, hematology including complete blood count with differential and platelet counts, and urinalysis), and the incidence of antibodies to etrolizumab.

Additional details will be provided in the SAP.

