6.5.1 Adverse Events

Verbatim descriptions of treatment-emergent adverse events will be coded and their incidence will be summarized by treatment arm, as appropriate. A treatment-emergent adverse event is defined as any new adverse event reported or any worsening of an existing condition on or after the first dose of study drug. In addition, separate summaries will be generated for serious adverse events, deaths, and adverse events leading to discontinuation of study drug. Adverse events will be summarized by mapped term, appropriate thesaurus level, and toxicity grade.

Analyses will be performed for:

- Systemic hypersensitivity events
 - Specific analyses will be performed for anaphylactic reactions using the anaphylactic reaction Sampson's criteria (see [Appendix 8](#)).
- Serious infections
 - The frequency of serious infections, in particular GI infections, will be summarized for each treatment arm.
- Opportunistic infections
 - The occurrence of opportunistic infections will be summarized for each treatment arm.
- Malignancies
 - Events that occur in the Neoplasms, Benign, Malignant, and Unspecified (Including Cysts and Polyps) System Organ Class will also be summarized for each treatment arm.
- Injection-site reactions
 - The frequency of injection-site reactions will be summarized for each treatment arm.

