### **4.6                SAFETY ANALYSES**

Data reported during the Induction Phase using the induction safety population will include data for all patients enrolled into the Induction Phase, up until they are randomized into the Maintenance Phase. For patients who are not randomized into the Maintenance Phase, data will be reported up until the patient completes/withdraws from the study. If a patient is ongoing in the Induction Phase due to being in safety follow-up at the time of the primary data analyses, all available data at time of the primary analyses CCOD will be reported.

Data reported during the Maintenance Phase will include data for all patients in the maintenance safety population up until the patient complete/withdraws from the study. All safety analyses using the maintenance safety population data will be reported from baseline. Baseline is defined as the last available assessment prior to first receipt of study drug at the beginning of the Induction Phase. If a patient is ongoing in the Maintenance Phase due to being in safety follow-up at the time of the primary data analyses, all available data at time of the primary analyses CCOD will be reported.

Further details of the safety analyses are included in the project SAP, Section 4.7.

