- Injection site reactions – Events identified using the eCRF tick box indicating an Injection site reaction AND/OR events occurred in the MedDRA Injection Site Reaction High Level Term (HLT) using both primary and secondary coding.

Outputs will be summarized using the safety population split by treatment arm and cohort as appropriate.

Summaries of AEs will be generated to summarize the incidence of treatment-emergent AEs only. Treatment-emergent events are defined as any new AE reported or any worsening of an existing condition on or after the first dose of study drug. If the onset date of the AE is prior to the day of first dose, the AE will be considered treatment-emergent only if the most extreme intensity is greater than the initial intensity (i.e., the intensity for a given AE increases and its end date is on or after the date of the first dose). Non-treatment emergent AE's collected in the database will also be reported separately, for each individual CSRs.

For each treatment group, the incidence count for each AE preferred term will be defined as the number of patients reporting at least one treatment-emergent occurrence of the

event (multiple occurrences of the same AE in one patient will be counted only once). The proportion of patients with an AE will be calculated as the incidence count divided by the total number of patients in the population. Each table will also present the total number of AEs reported where multiple occurrences of the same AE in an individual are counted separately.

The rate per 100 patient years and 95% CIs will be summarized by treatment group for studies (GA28950, GA29102, GA29103, GA28948, and GA28949). Rates will be calculated for AEs, SAEs, and other AE grouping as appropriate. The rate of AEs per 100 patient years is calculated as:

$$= \frac{\text{Total Number of AEs}}{\text{Total Number of Patient Years at Risk}} \times 100$$

All summaries and listings of AEs will be based on the induction safety population or the maintenance safety population and listed in the List of Planned Outputs (LoPO).

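### Non-serious worsening of an adverse event still open at randomisation carries no date, so its worst grade cannot be placed in Induction or Maintenance from the fields the Protocol specifies

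*Protocol*

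**What the plan says.** **Recording.** Protocol 5.3.5.3 says of persistent events: "Such events should be recorded only once on the Adverse Event eCRF". It continues: "The initial severity (intensity or grade) of the event will be recorded at the time the event is first reported", and then "If a persistent adverse event becomes more severe, the most extreme severity should be recorded on the Adverse Event eCRF". If the event turns serious, the site updates the record, "providing the date that the event became serious and completing all data fields related to serious adverse events". There is no matching request for the date of a grade increase. Protocol 5.5.1 asks for dated resolution. Sections 5.3.5.4 and 5.3.5.5 refer persisting laboratory and vital-sign abnormalities to the same rule.

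**Reporting.** Protocol 6.5 states: "Separate summaries of adverse events will be provided for the open-label Induction Phase and the Maintenance Phase". Section 6.5.1 defines a treatment-emergent event as "any new adverse event reported or any worsening of an existing condition on or after the first dose of study drug" and plans summaries by toxicity grade. Study SAP 4.6 includes Induction safety data "up until they are randomized into the Maintenance Phase", but reports the safety analyses of the Maintenance safety population from a baseline set before the first Induction dose. Project SAP Section 1 treats the two phases as independent studies for analysis.

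The only rule for undated worsening is in project SAP 4.7.1. It covers events with onset before the day of first dose and counts them as emergent if the most extreme intensity exceeds the initial one ("i.e., the intensity for a given AE increases and its end date is on or after the date of the first dose"). Study SAP 4.1.2.4 assigns each Maintenance patient to one arm.

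**The concern.** Phase-specific tables by grade need to know in which phase a grade was reached. The recording rule keeps the first and the worst grade but not when the worst was reached. In many trials this matters little, because treatment does not change during an event. Here every randomised patient comes from ten weeks of open-label etrolizumab, and half then switch to placebo. An event open across that switch can worsen on either side of it, on different treatments.

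At stake are two descriptive outputs: the Induction severity table, which has no control, and the Maintenance tables, which hold the study's only placebo-controlled safety comparison (about 105 patients per arm).

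**Working it through.** The plan states no figure on this point, so the check is made at record level. Take two patients, both later randomised to placebo, each with a non-serious event. The weeks are illustrative.

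| | Patient A | Patient B |
|---|---|---|
| Onset | Week 6 | Week 6 |
| Initial grade | 1 | 1 |
| Most extreme grade | 3 | 3 |
| End date | same day, after Week 30 | same day, after Week 30 |
| Date became serious | none | none |
| *Not asked for: when Grade 3 was reached* | *Week 9, open-label etrolizumab* | *Week 30, blinded placebo* |

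The five requested fields are identical. Now apply the reporting rules.

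1. **Induction table.** Onset at Week 6 brings both events in. The documents do not say which grade to tabulate. The most extreme grade is right for A and wrong for B; the initial grade is right for B and wrong for A. No choice is right for both.

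2. **Maintenance table, from-baseline sentence in study SAP 4.6 read literally.** Both appear under placebo at Grade 3. That is right for B but credits A's open-label grade to the blinded period.

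3. **Maintenance table, with the project SAP 4.7.1 rule re-anchored to the first Maintenance dose.** Extreme 3 exceeds initial 1 and the end date is later, so both count as emergent. An event that peaked at Week 9 and ended at Week 14 would pass the same test.

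**What can be placed.** Events resolved before randomisation, events with onset after it, and worsening that makes the event serious. Grade 4 and 5 events must be reported as serious (Protocol Table 6, footnote d). The residue is non-serious rises, mainly to Grade 2 or 3, in events open at randomisation.

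**Effect on the arm comparison.** Let a proportion b of each arm carry a given grade from Induction, and let p be the proportion reaching it after randomisation, independently of b. The table then shows b + (1 − b)p in each arm. The difference becomes (1 − b)(p_etrolizumab − p_placebo), and the ratio moves towards 1. Randomisation makes b equal in expectation across arms, so the effect is dilution and noise.

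**Scale.** The documents give no adverse event rates or durations. Purely as an illustration, assume that 25–40% of 210 randomised patients have an open event and 10–20% of those later rise by at least one grade. Then 210 × 0.25 × 0.10 = 5.3 and 210 × 0.40 × 0.20 = 16.8, so about 5 to 17 patients across both arms, before removing rises that become serious and are dated. Neither input has a source in the documents, so this is not an estimate.

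**The case against.** The strongest reply is that this is a narrow gap in descriptive tables. The most important worsening is dated through the seriousness rule, and serious events and events of special interest also need follow-up reports within 24 hours (Protocol 5.4). Laboratory abnormalities have their own worst-grade summary (project SAP 4.7.2). No hypothesis test or decision rule uses these grades. All of that stands and limits the point.

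It also stands that Protocol 5.3.5.3 instructs sites and is not a field list. The Adverse Event eCRF, its Help Text and the list of planned outputs are not in the documents, so a grade-change date may already exist. The claim is therefore limited to the fields the Protocol specifies. For the same reason, it cannot be said that the Induction table will show the later grade, only that it may. Even with such a field, the SAP lacks a rule for worsening after randomisation.

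A reader might go further in three ways that the documents do not support:

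- **Events land in the wrong arm.** Arm is assigned per patient by the treatment most often received in Maintenance (study SAP 4.1.2.4). A missing grade date does not change it.
- **Worsening is lost from the Maintenance comparison.** Under both readings in the working the event is included. It would drop out only if Maintenance tables counted by onset date alone, which the SAP does not say. The supported problem is over-inclusion.
- **The arm comparison is biased towards one treatment.** Grades reached before randomisation are balanced in expectation.

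**Conclusion.** The point holds in a limited form. From the fields the Protocol specifies, a non-serious grade increase in an event that begins in Induction and is open at randomisation cannot be placed before or after randomisation. Following the stated recording rule can therefore put a grade in the wrong phase. For a patient randomised to placebo, that means against the wrong treatment.

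The Induction severity table may be overstated, and the Maintenance comparison is diluted. Part of the Maintenance mixing comes from the from-baseline sentence itself, whose meaning is unclear: it may set the counting window, or only the reference for change. Without dates, however, the mixing cannot be undone for events open at randomisation.

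The number affected is unknown. A reader might set the illustrative 5 to 17 patients beside the number of Grade 3 or higher events expected per arm and call them similar. That comparison fails: the first counts any one-grade rise over both arms, the second only Grade 3 or higher in one arm. The conclusion assumes that the eCRF collects no more than Protocol 5.3.5.3 asks for. This is a cheap improvement to safety reporting and does not touch the efficacy conclusions.

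**What to change.** **Protocol 5.3.5.3.** For events still open at Maintenance randomisation, record the date of any later grade increase, or enter a linked new record from that date. If the date-field route is chosen, keep the highest grade reached up to randomisation as well; otherwise an intermediate Induction peak is overwritten. If the eCRF already captures this, cite the field.

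**SAP 4.6 and 4.7.1.** State that Induction tables use the highest grade dated before randomisation. Define Maintenance-emergent events as those with onset, or a dated grade increase, on or after the first Maintenance dose. Reconcile this with the sentence that reports Maintenance safety from the pre-induction baseline. Randomisation may occur from Week 10 and the first Maintenance dose is scheduled at Week 12, so also say where an increase between the two is counted.

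**Cost.** One eCRF date field (plus the retained grade if that route is used), a site memo, and a query on events open at randomisation for patients already randomised. No visit or procedure is added and clinical management does not change.
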